#### 4.3.2 Exclusion Criteria

1. Arterial insufficiency: Ankle-Brachial pressure index <0.7
2. Diabetes
3. Pregnancy
4. Crohn's Disease
5. Ulcerative Colitis
6. Infection or excessive colonization of ulcer in past 2 months
7. Patients whose neutrophil count is not within normal limits
8. Patients who have active Tuberculosis (positive QFT-G)
9. Patients currently being treated for malignancy
10. Patients with chronic or recurrent candidiasis infection
11. Patients who have inflammatory bowel disease (IBD)
12. Women of childbearing age
13. Any contraindication to therapy
14. Life expectancy of less than 6 months due to chronic illness

Any other condition as defined by the investigator which significantly impact the patient's suitability in this study such as the use of cytotoxic medication, inability to present to study visits due to distance.

## **5 SCREENING**

### **5.1 Screening Log**

Appropriately, qualified personnel at the trial site will screen patient health records for potentially suitable patients according to the eligibility criteria in the protocol. The trial site will then record de-identified information relating to each patient screened on the screening log (including ineligible patients) screening will continue until the target population is achieved. The screening log will be requested by the Sponsor on a regular basis for the purpose of monitoring accrual.

### **5.2 Informed Consent**

Written Informed consent from each patient must be obtained prior to initiating any study procedures in accordance with the ICH GCP. All potential study participants will be given a copy of the HREC approved Participant Information Sheet and Consent Form to read and discuss with family, general practitioners, specialists etc. The investigator will explain all aspects of the study in lay language and answer all questions regarding the study prior to signing consent. If the patient decides to participate in the study, they will be asked to sign the Informed Consent documents. One photocopy of each of the Participant Information Sheets and signed Informed Consents must be given to the patient to keep, the originals must be retained in the Investigator Site File. The completed and signed Informed Consent documents for all patients at the site must be available in the case of data audits. Patients who choose not to participate or who withdraw from the study will be offered appropriate treatment options reflecting the current standard of care without prejudice.

### **5.3 Participation in Other Research**

Participation in other research will be considered on a case by case basis by the Trial Management Committee.

## **6 ENROLMENT AND RANDOMISATION**

Every patient will undergo a period of 4 weeks of standard of care treatment and the ulcer will be measured at the start and end of this period.

Only patients who do not respond to standard of care therapy with less than 20% wound size reduction will be enrolled.

Following written informed consent, cohort of patients with chronic venous ulcers (n = 28) will be randomly assigned to treatment and placebo groups, both receiving concomitant compression treatment and standard dressing and therapy of wounds.

Patients will be stratified according to wound duration more or less than 6 months.

Randomisation will be done with a prevalidated computer program and participants will be stratified by ulcer duration ( $\leq 6$  months or  $> 6$  months) with permuted blocks (block sizes 4), because this criteria is a known predictor of ulcer healing.

Ixekizumab or placebo will be injected subcutaneously (prefilled syringe format) in two 80 mg injection at week 0, followed by single 80mg injections at weeks 2, 4, 6, 8, 10 and 12.

This corresponds to standard dosing regimen performed in psoriasis.

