## 2.3 Endpoints

### 2.3.1 Primary Endpoints

The primary endpoints are

- A 40% reduction in ulcer size at 12 weeks as compared to initial size. Size changes are measured using digital 3D photography and wound size evaluation device. It is expected that significantly more patients will achieve the primary end-point at 12 weeks in the Ixekizumab group compared to the placebo group.

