## 3 TRIAL DESIGN

Patients with a diagnosis of venous ulcer at the participating wound clinics will be considered and treated with standard compression therapy and dressing for 4 weeks. Those not responding to treatment with wound surface reduction <20% will be included and randomly assigned, using double blind technique, to treatment and placebo groups. All participants will receive standard of care treatment for chronic, non-healing wounds, comprising compression dressings changed as required. In addition to standard of care treatment, participants will receive either Ixekizumab or placebo via subcutaneous injection.

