#### **4.3.1 Inclusion Criteria**

1. Aged 18 years or older.
2. Patients who are willing to read or comprehend and signed a voluntary consent for research.
3. Patients with at least one venous leg ulcer defined as any break in the skin that had either been present for longer than 6 weeks or occurred in a person with a history of venous leg ulceration. Ulcers are judged purely venous if no other cause is suspected. The ulcer is required to be venous in appearance (moist, shallow, and of an irregular shape) and to lie wholly or partly within the gaiter region of the leg where varicosities or purpuric and pigmented skin can be identified.
4. Patients with Chronic Venous Ulcers that have failed to respond (<20% closure) to Standard Therapy including Compression 4 weeks

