### 9.2 Analysis of the Objective

Primary objective

- To compare the proportion of patients achieving a 40% reduction in wound size at week 12 between Ixekizumab and placebo groups.

Secondary Objective

- To compare the average wound size reduction in treated versus placebo group.
- To compare the number and proportion of patients achieving wound closure.
- To compare in an actuarial survival analysis the time to closure between placebo and treatment group.
- To compare average pain score and reduction in pain score at 12 weeks (Pain score 0-10) between placebo and treatment group.
- To compare average Quality of life (QOL) (measured by DLQI) and improvement in QOL at 12 weeks between placebo and treatment group.
- Compliance with compression will be compared as a patient reported outcome.

\*these biological endpoints will depend on availability of funding

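### The run-in entry rule (<20% in 4 weeks) and the primary response (40% at 12 weeks) overlap on a common rate: some eligible ulcers reach the response on an unchanged course, which may dilute the contrast but does not bias it

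*Protocol*

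**What the plan says.** Three sections of the protocol state the entry rule consistently. Section 3: "Those not responding to treatment with wound surface reduction <20% will be included and randomly assigned". Section 4.3.1 requires ulcers that "failed to respond (<20% closure) to Standard Therapy including Compression 4 weeks". Section 6: "Only patients who do not respond to standard of care therapy with less than 20% wound size reduction will be enrolled". For the 4-week run-in, Section 6 also says that "the ulcer will be measured at the start and end of this period".

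The primary endpoint in Section 2.3.1 is "A 40% reduction in ulcer size at 12 weeks as compared to initial size", and the primary objective in Section 9.2 is "To compare the proportion of patients achieving a 40% reduction in wound size at week 12 between Ixekizumab and placebo groups". Compression and standard wound care continue in both arms after randomisation (Sections 3 and 6). Randomisation is stratified by ulcer duration only.

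Sections 9.1 and 9.3 name ANOVA for the comparison of wound size. The protocol gives no expected placebo responder rate and no distribution of run-in change, and it does not relate the two thresholds to each other.

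**The concern.** The entry cut-off covers 4 weeks and the response cut-off covers three times as long. Twenty per cent in 4 weeks is a faster pace than 40% in 12 weeks. The upper part of the eligible range therefore holds ulcers that count as failing standard care at entry and as responders at week 12, even if nothing about their healing changes.

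Such ulcers respond in either arm, so they add nothing to the difference in responder proportions. They lift the placebo rate and shrink the contrast. With 28 patients in two equal groups there is little room for that. The run-in change that identifies them is measured under Section 6, but the protocol uses it only to decide entry, and the ANOVA that it names for wound size does not adjust for it.

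**Working it through.** **The plan's own figures.** The protocol gives no figure for natural-course response, so there is none to reproduce on this point. Its only power figure is the 85% in Section 9.1, for an improvement of 40% with SD 20%. Read as a difference of 40 with SD 20 and 14 per arm, this gives z = 40 / (20 × √(2/14)) = 5.29 and power of about 99.96%, not 85%. That is a separate matter, and nothing below depends on it.

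**Inputs.** Entry: reduction x < 20% over 4 weeks (Sections 3, 4.3.1, 6). Response: at least 40% at 12 weeks (Sections 2.3.1, 9.2). Assumption: the ulcer keeps its run-in rate for three further 4-week periods, with size counted from randomisation.

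**Reduction at week 12 under three healing models**

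- Constant proportional rate: 1 − (1 − x)³. At x = 20%: 1 − 0.8³ = 48.8%.
- Constant edge advance of a round ulcer, with r = √(1 − x): 1 − ((4r − 3)/r)². At x = 20%: r = 0.894, giving 58.3%.
- Constant area loss: 3x/(1 − x). At x = 20%: 0.6/0.8 = 75.0%.

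| Run-in reduction x | Proportional | Edge advance | Area loss |
|---|---|---|---|
| 10% | 27.1% | 29.8% | 33.3% |
| 15% | 38.6% | 44.3% | 52.9% |
| 19% | 46.9% | 55.6% | 70.4% |
| limit, 20% | 48.8% | 58.3% | 75.0% |

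**Run-in reduction that carries through to exactly 40%**

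- Proportional: 1 − 0.6^(1/3) = 15.7%.
- Edge advance: 13.5% (solved numerically).
- Area loss: 0.4/3.4 = 11.8%.

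If initial size in Section 2.3.1 means the start of the run-in, the span is 16 weeks and the overlap is wider: 1 − 0.6^(1/4) = 12.0% (proportional) or 0.40/4 = 10.0% (area loss).

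**Share of enrolled patients affected.** The documents give no distribution of run-in change, so this rests on assumption.

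- Uniform from −20% to +20%: (20 − 15.7)/40 = 11%, (20 − 13.5)/40 = 16%, (20 − 11.8)/40 = 21%.
- Normal, mean 0-10%, SD 15-20%, truncated at 20%: from 6% (mean 0, SD 15%, proportional) to 27% (mean 10%, SD 15%, area loss).
- If every enrolled ulcer shrank at least slightly (uniform 0 to 20%), the share would be higher, 22-41%. This shows how far the answer depends on the assumption.

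**Effect on the contrast.** If a share s of both arms responds regardless, the difference in responder proportions is multiplied by (1 − s). A 40-point difference among the other patients becomes 40 × 0.94 = 37.6 points at s = 6% and 40 × 0.73 = 29.2 points at s = 27%. As an illustration, take 14 per arm, a two-sided Fisher test and an assumed 20% placebo response among the other patients. Power is 44% at s = 0, 31% at s = 11% and 24% at s = 21%.

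**The case against.** The strongest reply is that nothing is misstated. The three sections agree on the entry rule, and no section claims that enrolled ulcers cannot shrink on compression. A randomised, blinded placebo arm exists to measure natural-course response, and any responder endpoint with a non-zero placebo rate has this feature. All of that stands. A reader might infer that the overlap biases the trial or could create a false positive. The documents do not support that: both arms draw from the same eligible population, and success is defined by the comparison of proportions, not by any one patient's response.

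A reader might also point to chance imbalance, since each such patient is 1/14, or about 7 points, of an arm's responder rate. At this size that is true of any unstratified prognostic factor, and the test's type I error already allows for it. It is not a separate fault.

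The size is also open to challenge. A constant rate is an assumption, the two faster models have no support in the documents, and under the proportional model only the band from 15.7% to 20% is affected. This stands, and it is why the share is given as a range under stated assumptions.

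Finally, covariates and supportive analyses are commonly left to a statistical analysis plan, which is not at hand. The absence of a covariate is therefore not the finding. What stands is that the protocol itself fixes two overlapping thresholds and names ANOVA for wound size, although it already requires the measurement that would sharpen that analysis.

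**Conclusion.** The point holds as a limited design weakness. The entry and response thresholds overlap under all three healing models: run-in reductions from about 12-16% up to the 20% limit lead to a primary response on an unchanged course. Ulcers at 10% or below do not reach it when size is counted from randomisation (27-33%).

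The consequence is a possibly higher placebo response and a diluted contrast, not bias. The affected share is unknown: about 6-27% under the uniform (−20% to +20%) and truncated normal assumptions. A reader might go further and conclude that the population is not treatment-resistant, or that a responder result would mean little. Neither follows, because the documents do not show how many enrolled ulcers lie in the upper band or whether their rates persist.

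**What to change.** 1. In Sections 9.1 and 9.3, replace the unadjusted ANOVA of ulcer size reduction with an ANCOVA that includes run-in percentage change as a continuous covariate. The cost is one degree of freedom (28 − 2 = 26 becomes 25). The gain depends on how strongly run-in change predicts the outcome: with correlation ρ, residual variance falls by the factor 1 − ρ². This sharpens the continuous comparison; it does not undo dilution of the primary responder comparison.

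2. Record the start and end run-in measurements in the CRF, by the same method as the endpoint. Section 6 requires them, but the Section 7.1 table shows no ulcer assessment in run-in weeks 1-4, and Section 6 names no method, while Section 2.3.1 specifies 3D photography. The table also places consent after the run-in, so consent must cover use of these measurements. The cost is a CRF field and consistent measurement.

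3. Optionally, add a supportive responder analysis against each patient's own projected run-in course. Count a patient only if the week-12 area meets the primary definition and is also at least 40% below the projection. Both conditions are needed. For an ulcer that grew 20% in the run-in, the proportional projection is 1.2³ = 1.73 times its size at randomisation, and 0.6 × 1.73 = 1.04, so an ulcer that merely stayed the same size would pass the second condition alone.

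4. Ask the sponsor to reconcile or justify the two thresholds on a common time scale, to state which measurement is the initial size, and to give the expected placebo responder rate. The cost is wording only. No new entry cut-off is proposed here. That is a clinical eligibility judgement with a real accrual cost: under the same assumptions, about 18-33% of otherwise eligible patients had run-in reductions between 10% and 20%, and the trial allows 9 months to enrol 28.

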## **4 PARTICIPANT SELECTION AND ELIGIBILITY**

### **4.1 Source of participants**

Participants will be recruited for the study the Queensland Institute of Dermatology Brisbane and other reliable Wound Care Clinics in Brisbane.

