## 9 STATISTICAL CONSIDERATIONS

### 9.1 Statistical Analysis

Treatment effect on wound size will be tested between treatment and placebo groups and across wound types by ANOVA.

Estimated number of 28 patients in 2 equal groups gives an 85% power at a significance level of 0.05 to detect an improvement of 40% in wound healing rates at 12 weeks (20% standard deviation). Based on preclinical studies, a 50% improvement is expected.

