### **12.2.2 Serious Adverse Events (SAE)**

SAEs are to be reported by the trial site immediately and no more than 24 hours of being notified, from the commencement of injection until the last visit. Date of the SAE occurrence and date notified must be documented.

The investigator at the trial site is responsible for;

- grading the event according to the NCI CTCAE v 5.0
- identifying the seriousness of the adverse event
- identifying the causal relationship to the treatment and
- determining the expectedness according to the treatment

The investigator is also responsible for notifying responsible HRECs, Research Governance Officers or other appropriate regulatory authorities of the SAE according to local ethical and regulatory guidelines. They are also to follow up the event (with regular reporting) until resolved. Please see figure 1.

[figure not shown]
The Sponsor shall;

- Arrange for the trial chairperson and/ or a clinical reviewer to review the event and confirm causal relationship and expectedness
- Report applicable events to the regulatory authorities (e.g Therapeutic Goods Administration of Australia (TGA))

Notify all other participating investigators of any serious unanticipated related adverse events and any action taken

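### The protocol prints a single fixed block size of 4, so any allocation that becomes known also informs on its block-mates; the size belongs in a restricted document (minor)

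*Protocol*

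**What the plan says.** Section 6 (Enrolment and Randomisation) states "Patients will be stratified according to wound duration more or less than 6 months" and then that allocation is computer generated "with permuted blocks (block sizes 4". One size is given, with no variation and no statement that it is withheld from site staff. Section 9.1 gives the ratio: "Estimated number of 28 patients in 2 equal groups".

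Other sections that bear on the point:

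- Section 3 says that patients are "randomly assigned, using double blind technique, to treatment and placebo groups"; both arms receive subcutaneous injections.
- Section 4.1 draws patients from the "Queensland Institute of Dermatology Brisbane and other reliable Wound Care Clinics in Brisbane". Ulcer duration is the only stratum named.
- Section 4.3.2 ends with an open exclusion for any other condition that the investigator considers important. Section 8 allows treatment to be discontinued on the investigator's opinion.
- Section 13.5 makes one role at the named institute responsible for identification, recruitment, data collection, case report forms and follow-up.

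**The concern.** Stratum, ratio and block size together describe the whole restriction on the list. While no allocation is known, this tells an investigator nothing. Once one is known or correctly guessed, the published size turns it into information about other patients in the same block, some of them perhaps not yet enrolled.

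Section 13.5 puts recruitment and follow-up in the same hands, so a suspected allocation could affect who is excluded under the open clause in Section 4.3.2, or who is discontinued under Section 8. With 28 patients, one event touches up to three others, 3/28 = 11% of the trial. Sites gain no operational benefit from knowing the size.

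**Working it through.** The plan gives no figure for predictability, so there is none to reproduce.

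**Inputs from the protocol.** Block size 4 and two strata (Section 6); 28 patients in two equal groups (Section 9.1). **Assumptions.** The protocol gives no stratum shares. Predictability is computed for 14 patients per stratum, balance for an expected 50:50 split between strata. Varying sizes are drawn with equal probability, and the guesser knows only the set of sizes.

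**One block of four.** There are 4!/(2!·2!) = 6 possible orders.

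1. One allocation known, say A first: AABB, ABAB and ABBA remain. Any given block-mate is B in 2 of the 3, so the probability of the other arm is 2/3.
2. Two known and alike: the remaining two are fixed. Two known and different: the remaining two stay at 1/2 each.
3. All earlier allocations known: AABB has 2 determined positions, ABAB and ABBA have 1 each. With the mirror images this is 8 of 6 × 4 = 24 positions, or 1/3.

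**A stratum of 14 (three full blocks and two patients of a fourth).**

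- Determined share: 3 × (4/3) / 14 = 4/14 = 29%.
- Next patient on the other arm after one allocation is revealed at random: of 13 adjacent pairs, 10 lie within a block and 3 straddle two blocks, so (10 × 2/3 + 3 × 1/2)/13 = 0.63.
- Correct guesses with all earlier allocations known: a full block yields 1/2 + 2/3 + 2/3 + 1 = 2.83 and the part block 1/2 + 2/3 = 1.17, so (3 × 2.83 + 1.17)/14 = 69%.

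**Alternatives.** The fixed-4 predictability figures above agree with the simulation that gave the other rows and all the balance figures:

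| Block sizes | Next patient on other arm | Correct guesses, all earlier known | Fully determined, all earlier known | Arm difference ≥2 | Arm difference ≥4 |
|---|---|---|---|---|---|
| 4 | 0.63 | 69% | 29% | 37% | 1.3% |
| 2/4 | 0.68 | 72% | 10% | 36% | 0.3% |
| 4/6 | 0.61 | 68% | 6% | 45% | 2.3% |
| 4/6/8 | 0.59 | 67% | 3% | 49% | 4.2% |

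With stratum shares of 30:70, the chance of a difference of 2 or more is almost the same (38% for fixed 4, 45% for 4/6).

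**Price of imbalance.** Relative efficiency is (4/28)/(1/n₁ + 1/n₂). For 13/15 it is 0.1429/0.1436 = 0.995, a loss of 0.5%. For 12/16 it is 0.1429/0.1458 = 0.980, a loss of 2.0%.

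**The case against.** The strongest reply is that a fixed block of 4 is a defensible choice for balance in a small masked trial, and that the leak needs a trigger which the protocol does not describe. That stands. Several stronger readings are tempting, and the document does not support them:

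- *Serious adverse event handling reveals allocations.* Section 12.2.2 has the sponsor "Notify all other participating investigators of any serious unanticipated related adverse events and any action taken". It mentions neither treatment codes nor unblinding. No unblinding rate is given anywhere, so only a conditional probability can be stated, not an expected number of leaks.
- *A third of the allocations are predictable.* That figure requires every earlier allocation in the block to be known, which would amount to an open-label trial.
- *A clinician's judgement of the primary endpoint is exposed.* Section 2.3.1 specifies digital 3D photography and a wound-measuring device. This does not exclude bias, but it weakens the assessment route.
- *Selection is unconstrained.* Entry requires less than 20% closure after four weeks of standard therapy, and Section 4.3 rules out waivers. Only the open clause of Section 4.3.2 leaves room.
- *Every investigator can follow the sequence.* If several clinics share a stratum list, each sees only part of it and cannot tell who the block-mates are.
- *Varying the sizes removes the leak at no cost.* The table shows otherwise: no block scheme brings the next-patient probability to 0.50, and larger blocks cost some balance.

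What survives is that the size is printed where investigators read it, and that discretion, recruitment and follow-up meet in one role.

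**Conclusion.** The point holds as a minor design improvement. The protocol contains no error or contradiction here. The move from 1/2 to 2/3 is exact for a block of four. Its practical effect depends on three conditions: an allocation becoming known despite the blind, the investigator knowing the order of entry within the stratum, and discretion being exercised on that knowledge. The documents do not allow the probability of any of these to be estimated.

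The main gain from undisclosed sizes is the loss of certainty about particular patients. Average guessability hardly changes. The figures for varying blocks rest on the assumed stratum sizes and on equal-probability draws.

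**What to change.** In Section 6, delete the block size and state only that allocation uses permuted blocks stratified by ulcer duration. Record the size in a restricted randomisation document that site staff cannot see. This costs one phrase; sample size and balance are unaffected. By itself it leaves the list as predictable as before to anyone who learns or infers the size, but it removes the published key.

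Optionally, generate the list with undisclosed, randomly varying sizes of 4 or more, for example 4 and 6. This needs a new list before the first randomisation and accepts the slightly worse balance shown above. Do not mix 2 and 4: this lowers the determined share but makes the next patient easier to predict than a fixed block of 4 does.
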